# Clinical Investigation Plan (CIP)

Study Name: VivaSight-DL study (CIS-009)  
Ethical committee number: S-20180081

CLI-000427

Rev. 02

- Number of intubation attempts
  - Intubation attempt is defined as the number of intubation attempts until successful intubation is accomplished. If the endotracheal tube is incorrectly placed and the tube is withdrawn from the subjects throat it counts as one attempt.
  - If more than three intubation attempts are used the intubation is defined as a failure and the subject is excluded from the study.
- Number of times incorrect placement of the tube is prevented during intubation
  - Prevention of repositioning is a corrective action that ensures optimal ventilation of the subject without having to move the tube after the bronchial cuff is inflated. An example of a corrective action during intubation could be change of the tube direction if it starts to enter the right main bronchi instead of the left main bronchi when advanced down the throat.
- Number of times the tube needs to be repositioned during intubation
  - In this study, repositioning is defined as the action where the bronchial cuff needs to be deflated to move the tube into the right position.
- Number of times where the physician prevents repositioning of the tube during surgery
  - Prevention of repositioning is a corrective action that ensures optimal ventilation of the subject without having to move the tube after the bronchial cuff is inflated. An example of a corrective action during surgery could be optimization of the cuff sealing by deflating and inflating the cuff without moving the tube.
- Number of times the tube needs to be repositioned during surgery.
  - In this study, repositioning is defined as the action where the bronchial cuff needs to be deflated to move the tube into the right position.
- Repositioning time (seconds) during surgery
  - In this study, repositioning is defined as the action where the bronchial cuff needs to be deflated to move the tube into the right position.
  - Time starts: when the syringe is attached to the valve to deflate the bronchial cuff
  - Time stops: when correct bronchial cuff placement is verified by capnography
- Rate of restriction on the surgical procedure during repositioning of the tube
  - One of the following statements is chosen:
    - Not restricted
      - The surgical procedure is not restricted at all, the surgeon continues to work full speed
    - Restricted

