## 6.5 Exclusion during the examination

The subject can be excluded during the investigation if:

- The subject or legal representative decides to abort the study
- The subject is assigned to a physician with experience in > 50 DLT intubations in patients
- The investigator considers it necessary to change the type of endotracheal tube used for the procedure
- The investigator assess that it is necessary to exclude the subject from the investigation to ensure safety of the subject

If a subject withdraw from the study before the study randomization envelopes seal is broken (example no. 10), then the next subject will continue with consecutive subject number (no. 11).

If the subject is excluded *after* the procedure is started, he or she will be treated and receive routine treatment. Reason for exclusion will be stated in the CRF but otherwise data will not be collected in the CRF.

If the subject is excluded *before* the procedure is started, he or she will receive routine treatment. Reasons for exclusion will be stated in the CRF but otherwise data will not be collected in the CRF.

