### 7.8 Extubation

Prior extubation of the subject, the tracheal and endobronchial cuffs is deflated completely by inserting a syringe into valve housing and removing the gas mixture, until a definite vacuum is noted in the syringe and the pilot balloon collapsed. The extubation is performed slowly.

- *Information about the extubation must be recorded in the CRF (smooth extubation, did the subject cough, did the subject complain of throat pain).*
- *General information (adverse events, complications, deviations from protocol) about the procedure must be recorded in the CRF after extubation is completed.*

For the test group, the single use adaptor cable is disconnected from the aView monitor after extubation, and the aView monitor is turned off by pressing the power button for at least two seconds. The DLT (VivaSight-DL or Shiley) and single-use accessories are discarded after use.

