## 13.2 Investigator requirements

Investigator must record and document all adverse events in the Adverse Event Form.

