### Data collection

Type of surgery	Date of surgery	Knife start (hh:mm)	Knife end (hh:mm)
 Open  Keyhole			

**Intubation** (the period from the direct laryngoscope is introduced into the subject's mouth until correct bronchial cuff placement is verified by capnography)

Bronchoscope use (n)	Repositioning prevented (n)	Tube repositioned (n)	Intubation attempts (n)	Intubation time (sec)
				sec.

Cormack-L classification	Smooth intubation?	Need to bend tube?	Resistance during tube placement?	Need of suction after tube placement?
 1  2  3  4	 Yes  No			

Bronchial cuff pressure	Tracheal cuff pressure	Comments:
Cm H 2 O	Cm H 2 O	

**Surgery** (the period from correct bronchial cuff placement is verified by capnography until the DLT exits the subject's mouth)

Bronchoscope use (n)	Repositioning prevented (n)	Tube repositioned (n)

Repositioning of tube	Time used to reposition the tube	Rate of restriction on the surgical procedure	Responsible anesthesiologist assisted	Time spend by responsible anesthesiologist
1 st repositioning	sec	 Not restricted  Restricted  Completely restricted	 Yes  No	sec
2 nd repositioning	sec	 Not restricted  Restricted  Completely restricted	 Yes  No	sec
3 rd repositioning	sec	 Not restricted  Restricted  Completely restricted	 Yes  No	sec

Extubation of the subject	Smooth extubation?	Did the subject cough?	Did the subject complain of throat pain?
	 Yes  No	 Yes  No	 Yes  No

Comments:

Any adverse events/adverse device effects?		
Yes	No	If yes: please specify (if SAE or SADE please fill out SEA or SADE form):

Any complications in relation to airway management?		
Yes	No	If yes: please specify:

Any general complications?		
Yes	No	If yes: please specify:

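### Section 6.5 closes the CRF for subjects excluded after the procedure has started, so CRF safety fields are selectively blank and non-serious adverse events risk under-recording

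*Combined protocol and SAP*

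**What the plan says.** Section 6.5 gives the rule for a subject excluded once the procedure is under way: "Reason for exclusion will be stated in the CRF but otherwise data will not be collected in the CRF". An almost identical sentence covers subjects excluded before the procedure. The listed grounds include "The investigator assess that it is necessary to exclude the subject from the investigation to ensure safety of the subject" and "The investigator considers it necessary to change the type of endotracheal tube used for the procedure". Section 4 adds another: "If more than three intubation attempts are used the intubation is defined as a failure and the subject is excluded from the study".

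Safety information has three routes:

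- **CRF.** Section 7.8: "General information (adverse events, complications, deviations from protocol) about the procedure must be recorded in the CRF after extubation is completed". The CRF page (Appendix V) has boxes for adverse events, airway complications, general complications, smooth extubation, cough and throat pain. Beside the adverse event box it adds: "if SAE or SADE please fill out SEA or SADE form".
- **Adverse Event Form.** Section 13.2: "Investigator must record and document all adverse events in the Adverse Event Form". The same section requires every adverse event to reach the sponsor within three calendar days. Section 18.6 lists these forms separately from the CRFs.
- **Subject questionnaire.** Under section 7.9 a research assistant contacts the subject within 48 hours of surgery about quality of life and side effects (Appendix VI).

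On data up to dropout, section 6.4 stores a withdrawn subject's data but does not analyse them. Section 18.3.2 keeps intermediate dropouts out of the primary analysis but otherwise uses their data up to dropout.

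**The concern.** Section 6.5 treats a patient who has already been exposed to the tube like one who never was. Safety, tube change and failed intubation are plausibly linked to airway difficulty or device performance, so closing the CRF at that point removes safety fields in a way that may depend on what those fields measure. The loss could differ between arms, in either direction.

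What is at stake is the descriptive safety comparison: complication and extubation findings by arm would describe only the procedures that stayed in the study. For non-serious adverse events the stake is completeness. The working document at the bedside points to the CRF, and section 6.5 closes the CRF.

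**Working it through.** **Plan's own figures.** The plan gives no adverse event rate and no expected number of exclusions after the start. Its only related number is the dropout allowance, which reproduces. Per arm: (0.23622 + 0.01087) × (1.96 + 1.28)² / (0.37234 − 0.01087)² = 19.852. Twice that is 39.70, rounded to 40, and 40 / (1 − 0.20) = 50. Nothing in this point changes that calculation.

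**What is recorded after a post-start exclusion, item by item.**

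| Item | Where the plan puts it | After exclusion |
|---|---|---|
| Airway and general complications | CRF (7.8, Appendix V) | Stopped by 6.5; no other form named for these fields |
| Smooth extubation, cough, throat pain at extubation | CRF (7.8, Appendix V) | Stopped by 6.5; no other form named |
| Serious adverse events | CRF box, SAE/SADE form, Adverse Event Form (13.2) | Separate forms still required |
| Non-serious adverse events | CRF box (7.8) and Adverse Event Form (13.2) | Form still required, but the CRF does not prompt for it |
| Side effects at 48 hours | Questionnaire (7.9, Appendix VI) | Not stated |

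A complication that meets the adverse event definition in 13.1 should also reach the Adverse Event Form. The structured CRF fields as a set are not restored by any other section.

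**Three rules for overlapping patients.** Section 6.5 says data are not collected, 6.4 says data already recorded are kept but not used, and 18.3.2 says they are used up to dropout. These cannot be set aside as different populations: the subject's own decision to stop is a listed ground in 6.5 and is also the withdrawal covered by 6.4. A patient excluded after intubation but before surgery falls under both 6.5 and 18.3.2.

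**Illustration only (assumed inputs).** Let e be the share of the 50 subjects excluded after the start, p = 10% the adverse event risk in retained subjects, and r the relative risk in excluded subjects. The true proportion is (1 − e)p + e·r·p, and the share of affected subjects who were excluded is e·r·p divided by that. The upper value of e is the plan's 20% allowance; p and r are assumptions.

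| e (subjects) | r | True proportion | Share among excluded |
|---|---|---|---|
| 4% (2) | 1 | 10.0% | 4.0% |
| 4% (2) | 5 | 11.6% | 17.2% |
| 10% (5) | 3 | 12.0% | 25.0% |
| 20% (10) | 1 | 10.0% | 20.0% |
| 20% (10) | 5 | 18.0% | 55.6% |

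Retained subjects show 10% throughout. Within one arm, if 2 of 25 are excluded, both with an airway event, and 2 of the other 23 also have one, the CRF shows 2/23 = 8.7% against a true 4/25 = 16%. One event is 1/25 = 4 percentage points. All these figures assume that no other route captures the excluded subjects' events, so they are ceilings for their inputs and not estimates.

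**The case against.** The strongest reply is that 6.5 restricts only the CRF. Section 13.2 requires all adverse events on a separate form and exempts no one, so a site can obey both sections at once. Investigators are trained on adverse event reporting at initiation, and the close-out visit checks adverse event documentation (9.1). Section 9.2 verifies adverse events and dropout against the medical record for 20% of subjects, and for all subjects if an inconsistency is found. The reason for exclusion, which is recorded, would often name the problem.

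Most of this stands, and it rules out some stronger readings that a reader might infer:

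- **That non-serious adverse events are lost, in contradiction of 13.2.** The duty in 13.2 survives exclusion. The risk is under-recording through an unclear route.
- **That excluded subjects are not owed the 48-hour questionnaire.** It is not part of the CRF and 6.5 does not stop it. The documents are silent.
- **That an interruption decision under section 14 would rest on a depleted record.** Serious events have their own forms, and device deficiencies have their own reporting route (7.3, 13.3).
- **That excluded patients are the ones most likely to have events.** This is plausible for safety, tube change and failed intubation. No figure in the documents supports it, and it does not fit exclusion by the subject's choice or because an experienced physician was assigned.

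The reply does not restore the complication and extubation fields, for which no other form is named. The safeguard in 13.2 is also less clear than it looks: 13.2 sets three calendar days for reporting to the sponsor, while 13.3 gives two days for serious and seven for other events.

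**Conclusion.** The point holds as a selective gap in CRF safety data, a risk of under-recording non-serious adverse events, and an unreconciled rule on data up to dropout. It does not hold as a demonstrated loss of adverse events or a strict contradiction of 13.2. Its size cannot be computed from the documents, and the illustrative figures should not be cited as an expected effect. That the gap is informative rests on the inference that safety, tube-change and failed-intubation exclusions are tied to airway or device trouble.

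The primary endpoint is bronchoscope use and side effects are tertiary, so the primary analysis and sample size are untouched. This is an inexpensive improvement worth making, and it is not a condition for the trial to proceed.

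**What to change.** - **6.5:** limit the rule against further CRF data to subjects excluded before intubation starts, using the start already defined in 7.5 (introduction of the laryngoscope).
- **Subjects in whom intubation was started:** complete the CRF adverse event, complication and extubation fields, the Adverse Event Form and the 48-hour questionnaire, and report them by allocated arm, unless consent to data collection is withdrawn.
- **CRF note:** change it to match 13.2, so that all adverse events, serious or not, go on the form.
- **6.4, 6.5 and 18.3.2:** reconcile them into one rule on whether data up to dropout are collected and in which analyses they are used. Reconcile the reporting times in 13.2 and 13.3 at the same time.

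The cost is some protocol wording, one CRF line, and a few extra forms and questionnaires. The fields, forms and contact already exist. The change concerns data collection only and leaves clinical care as it is.

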## 7. PROCEDURE

The participating site (OÜH, department V, section BTY) will receive the protocol, 40 VivaSight-DL, two aView monitors and CRF's. The specific VivaSight-DL and aView lot numbers or the Shiley Lot numbers will be collected in the CRF under product identification.

All investigators must sign the Secrecy Agreement and the Investigator Sponsor Agreement before participating in the study. In addition, all investigators must provide an updated CV.

Before participating in the study, all novice physicians will complete a simulation training course and experience at least 10 conventional DLT placements and three VivaSight-DL placements in manikin. Investigational product training will be recorded on a separate form and stored in the Sponsor File along with Secrecy Agreements, Investigator Sponsor Agreements, CVs and documentation on the Investigators experience in intubation.

# Clinical Investigation Plan (CIP)

Study Name: VivaSight-DL study (CIS-009)  
 Ethical committee number: S-20180081

CLI-000427

Rev. 02

The investigation procedure will contain the following sections:

1. Recruitment of subjects
2. Preparation of procedure
3. Induction of anaesthesia
4. Intubation
5. Surgery
6. Subject monitoring during the surgery
7. Awakening of subject and follow up
8. Collection of cost data

Before the investigation is initiated all investigators will be instructed in the study protocol. Subjects will be recruited, and Informed Consent will be obtained by Investigators (nurses or physicians with at least two years of experience in anesthesia). The data will be collected on a CRF (paper or electronic format) during the procedure, when the CRF is completed the principal investigator will check that it is filled out correctly and sign it. Prior to the investigation a pilot will be run to test the data collection method in practice and ensure that the involved parts are familiar with the protocol (see section 7.1).

## 7.1 Pilot study

The purpose of the pilot study is to test the protocol in practice and ensure that the procedures allows for a proper data collection. After ethical approval up to 10 subjects will be recruited as described in section 6.3 and 12 for the pilot study. The first subject will be allocated to receive single-lung ventilation using Shiley™ Endobronchial Tube. The pilot will follow the same procedures as described in the subsequent sections (section 7.2-7.9). During the pilot, double data recording will be performed by two independent individuals (a physician and an investigator or a research assistant). The collected data will be compared across the two individuals to ensure that data collection is aligned. In case a significant difference in the recorded data is found, the cause of the variation is investigated, and the data collection method is corrected to ensure a standardized procedure. If the data collection procedure is corrected, the pilot is repeated until the data collection method for the Shiley™ Endobronchial Tube is verified. However, a maximum of 5 subjects are included. After completing the pilot testing of the Shiley™ Endobronchial Tube protocol, the VivaSight-DL protocol is verified following the same procedures. The data recorded during the pilot study will not be included in the data analysis.

## 7.2 Recruitment of subject

Patient Information will be given during the preoperative visit with the anesthesiologist prior to the surgery. Subjects will be recruited, and Informed Consent will be obtained as described in section 6.4 and 12. After signing the informed consent, the subject is enrolled in the study. The investigator who obtained Informed Consent will write his/her name under “Centre Identification” and “Investigator’s name” and collect the following demographic data, airway assessment parameters and surgical information’s in the CRF under “Patient Information”:

- Age
- Gender
- Height
- Weight
- ASA class
- Indication for the surgery
- Date of enrolment
- Fulfilment of the inclusion/exclusion criteria

## 7.3 Preparation of the procedure

Latest on the day of the procedure, the subject will be assigned a physician who will perform the intubation. If the subject is assigned a physician with experience in > 50 DLT intubations in patients, the subject will be excluded from the study and receive the standard treatment. If the subject is assigned a physician with experience in < 50 DLT intubations, the subject will be randomized to receive single-lung ventilation using either VivaSight-DL (test group) or Shiley™ Endobronchial Tube (control group).

# Clinical Investigation Plan (CIP)

Study Name: VivaSight-DL study (CIS-009)  
 Ethical committee number: S-20180081

CLI-000427

Rev. 02

Before initiating the investigational procedure, the following information is recorded in the CRF:

- Investigator Name (under “Centre Identification”)
- Product Identification:
  - For test group:
    - VivaSight-DL Lot. No
    - aView Lot No
    - FOB brand and model
  - For control group:
    - Shiley Lot No
    - FOB brand and model
- Date of surgery (under “Data collection”)
- Type of surgery performed (under “Data collection”)

All equipment and all drugs needed for the entire procedure (anesthesia, intubation, surgery) is prepared and ready for use before anesthesia. In addition, a preparation table is set up in the operating room. The table will include the equipment needed for the intubation procedure, including:

- Puttable cloths
- Alcohol wipes
- Lubricant
- Antifogging agents
- Direct laryngoscope
- The intubation tube and accessories (e.g. adaptor, stylet and aView monitor for VivaSight-DL)
- Syringes

All essential equipment (e.g. laryngoscope handles, tubes) should have readily available back-up counterparts in case of unexpected failure. If anything is missing, it must be made available before the procedure is started.

The size of the double lumen tube is chosen prior preparation of the device. The ideal size of the tube result in a near-complete seal of the bronchial lumen without inflation of the cuff. After choosing the correct size, the device must be prepared following the manufacturer’s instructions and the function of the device must be checked in advance, to ensure that the tube is working properly. If a tube has a malfunction, it must be replaced before starting the procedure. This information will be collected in the CRF and for the Ambo products a device deficiency (DD) form must be filled out. The following sections will describe in detail how the test device or the comparative device should be prepared.

## 7.3.1 Preparation of test device

The steps described below must be followed when preparing the test device

1. Connect VivaSight-DL to the single use adapter cable. Be careful to align the white arrow on the single use adapter cable with the green arrow on the VivaSight-DL tube round connector.
2. Connect the single use adapter cable to the aView™ monitor, be careful to align the arrow on the cable with the arrow indicator on the aView™ monitor. Verify that all electrical connections are stable and secure.
3. Press the power button on top of the aView™ monitor for at least one second until a live image appears. The aView™ user interface will be ready after approximately one minute, when the hourglass symbol disappears.
4. Check that the two LEDs at the tip of the tube are illuminated. If they are not illuminated, replace the tube.
5. Verify that there is a stable image on the aView™ monitor (projected from the tip of VivaSight-DL). Then turn off the monitor again until immediately prior to intubation.
6. Test the cuffs for integrity by inflating and deflating them completely.
7. Become familiar with the feel of the blue and clear pilot balloons.

## 7.3.2 Preparation of control device

The steps described below must be followed when preparing the comparative device

1. Carefully remove the sterile endobronchial tube from its protective package.
2. Test the cuffs, pilot balloons and valves of each tube by inflation prior to use: Insert a Luer tip syringe into each cuff inflation valve housing and inject enough air to fully inflate the cuffs
3. After test inflation of the cuffs, evacuate completely all the air from the cuffs and remove syringe
4. Examine and familiarize yourself with the Right Angle Swivel Connector assembly and Carlens adaptor before beginning the intubation procedure. After determining which connectors are required, firmly seat them into the extension circuit of the anesthesia machine.

